### 10.3. Additional outcomes:

10.3.1. *Feasibility.* Descriptive demographic and clinical data will be compared across study groups to assess adequacy of randomization. Summary statistics (count data) will be recorded for patients across all 3 intervention arms to assess feasibility as (1) the enrollment rate (enrolled)/(enrolled+refusals) over each 12 month period; (2) protocol adherence (proportion of randomized subjects who receive 1 or more doses of the allocated intervention); and (3) fidelity of the intervention (defined as the proportion of high/low inulin allocated vs received and also categorically as receipt of 90% or more allocated doses of inulin across groups). Feasibility goals are as stated in Aim 1.

10.3.2. *Rates of pre-specified AEs.* There will be active ascertainment of AEs in the following categories, which will be compared between intervention groups. This will be done through the end of the intervention period (ICU Day 7) and also through Day 30/discharge to assess for delayed AEs.

- Stool frequency, measured by subject or nursing report by the number of spontaneous stools over the 24 hours preceding each assessment;
- Stool consistency, measured by subject or nursing report as an ordinal variable (0-4) over the 24 hours preceding each assessment;

- Abdominal bloating, measured by subject or nursing report as an ordinal variable (0-3) over the 24 hours preceding each assessment.
- Electrolyte abnormalities, measured by examining for differences in median values, minimum/maximum values, and proportions of values outside the normal range. This will be done for glucose, calcium, magnesium, phosphate, potassium, and sodium.
- Nausea, vomiting, obstruction, and abdominal pain. These will be recorded as present or absent based on bedside assessment of the subject or based on the nursing impression.
- Culture-proven infections, which will be considered both an AE and an outcome (see 10.3.4).

10.3.3. *Antibiotic resistance gene fraction on ICU Day 3.* DNA will be extracted from rectal swabs (MoBio PowerFecal, Carlsbad, CA) and assessed using multiplex quantitative PCR (Qiagen Cat. No. 330261, Valencia, CA) for 87 common antibiotic resistance genes. Within-individual differences in multiplex qPCR results will be compared from baseline to Day 3 both as summed changes and within relevant gene categories (e.g.,  $\beta$ -lactamase resistance genes) and compared between intervention groups.

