### 12. Enrollment strategy

Patients will be identified at the time of ICU bed allocation and screened for inclusion/exclusion criteria. After consultation with the treating ICU team, subjects who meet screening criteria will have the eligibility evaluation completed at the ICU bedside. This will be done after first obtaining agreement from the medical ICU attending of record that the patient/surrogate can be approached for the study. We anticipate that  $>50\%$  of patients will lack decision-making capacity and will accept consent from a surrogate in these situations, as previously described by our group. Issues related to altered capacity, privacy and time for decision-making, consent of LARs, and ongoing consent are discussed in detail in the **Human Subjects and Recruitment and Safety**

**Procedures** section. We expect that patients will usually be initially enrolled with surrogate consent. Patients who are on study will then be reassessed for capacity at each interaction, with the final determination of capacity made by the treating ICU team. When subjects regain capacity, they will make their own determination of whether or not to continue in the study. If subjects do not regain capacity by the time of hospital discharge, surrogate consent will be accepted as final. This approach, which we have used before, preserves complete patient autonomy while recognizing that the target population for the study is unlikely to have decision-making capacity at the time of ICU admission.

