### 13.3.1. Tolerability

Patients who are alert will be asked regarding abdominal bloating which will be graded on a 4-point Likert scale (0=none, 1=a little, 2=a moderate amount, 3=a lot/severe). When patients are not alert, this will be graded as “unable.” ICU nurses will be asked to grade the average consistency of stools within each preceding 24 hours on a 5-point scale (0=like water, 1=like porridge, 2=loose but with chunks, 3=formed, soft, 4=formed, hard). This information will also be recorded from the EMR into REDCap as a separate entry. When subjects have no stools within the preceding 24 hours, this will be recorded as “no stools.” The frequency of stools within the preceding 24 hours will be recorded as an integer at each study assessment. Again, this will be done based both on the nurse’s in-person report and separately based on EMR documentation.

ICU nurses will be additionally asked regarding the presence or absence of the following symptoms during the 24 hour period prior to each study assessment: nausea, vomiting, bowel obstruction, and abdominal pain. This data will be recorded categorically on the CRFs/REDCap and will appear on DSMO reports.

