#### **15. Safety and adverse events (AEs)**

Adverse health events, laboratory irregularities, and even death are expected in ICU patients with sepsis and it would be difficult or impossible to accurately document and label all adverse health events. This is a common problem faced by ICU trials. The solution recommended by academic critical care research groups (e.g., Cook *et al.*) is to pre-specify AEs of interest for careful monitoring. In keeping with this approach, this study will produce detailed reports of these AEs for the DSMC at standard intervals while only unanticipated problems that also meet criteria for serious adverse events (SAEs) will be reported to the DSMC in real time. AEs will be reported for all individuals who have received one or more doses of the intervention. This study has pre-specified AEs in the following categories.

- Bloating: graded 0-3 based on patient report: patient mean and maximum values will be reported;
- Stool consistency and frequency: graded 0-4 for consistency and with an integer denoting frequency over 24 hours based on nursing report. For each patient, mean and maximum values will be reported;
- Electrolyte imbalances: For each patient, the minimum and maximum values for serum calcium, magnesium, phosphate, potassium, and sodium will be reported. This will be done for the 7 days of the intervention period and separately from Day 7 through Day 30/discharge;
- Gastrointestinal AEs: the gastrointestinal AEs of nausea, vomiting, bowel obstruction, and abdominal pain will be recorded as present or absent for each assessment and separated from other AEs to improve early pattern recognition by the DSMO;
- Infections: Infections are both an AE and an outcome and will be adjudicated as previously described. For each infection, the date of the infection, suspected site, organism, and antibiotics received will be recorded. Infections will be further classified as MDR vs non-MDR using the criteria previously described;
- Death: death will be gathered from the hospital EMR, which interfaces with the social security death index.

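### Nausea and abdominal pain have no not-assessable code, so their rates and between-arm differences are probably understated by an unknown amount

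*Combined protocol and SAP*

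**What the plan says.** Section 13.3.1 sets the procedure: "ICU nurses will be additionally asked regarding the presence or absence of the following symptoms", over the 24 hours before each study assessment. The list is nausea, vomiting, bowel obstruction and abdominal pain.

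Section 10.3.2 describes the same four items with a wider source: "These will be recorded as present or absent based on bedside assessment of the subject or based on the nursing impression". It adds that "There will be active ascertainment of AEs in the following categories, which will be compared between intervention groups".

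Section 15 repeats the two-way coding ("nausea, vomiting, bowel obstruction, and abdominal pain will be recorded as present or absent for each assessment") and sets the reporting population: "AEs will be reported for all individuals who have received one or more doses of the intervention".

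Bloating is handled differently. Section 13.3.1 asks alert patients to grade it and then states: "When patients are not alert, this will be graded as" *unable*. Stool consistency likewise has a code for no stools in the window.

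On the population, section 12 anticipates that more than 50% "of patients will lack decision-making capacity and will accept consent from a surrogate in these situations".

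**The concern.** Vomiting and obstruction can be observed. Nausea and abdominal pain are mainly known from what the patient says. With only two codes, a nurse asked about a patient who cannot communicate has to guess, and absent is the likelier entry when nothing is seen. Reporting over all dosed patients then keeps those entries in the denominator as if they were informative.

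Safety is a stated purpose of the trial (section 5.2). These items go into the safety officer's reports (section 13.3.1), and section 15 separates them from other adverse events to help early pattern recognition. Under-recording moves the comparison towards no difference, which for a tolerability outcome is the falsely reassuring direction.

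**Working it through.** **1. The passages side by side.** The plan gives no expected rate, precision or power for nausea or abdominal pain, so there is no figure of its own to reproduce.

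| Item | Who is asked | Code when the patient cannot report |
|---|---|---|
| Bloating (13.3.1) | Alert patients | *Unable* |
| Nausea, abdominal pain (13.3.1) | ICU nurses | None stated |
| Nausea, abdominal pain (10.3.2) | Subject at the bedside, or nursing impression | None stated |
| Nausea, abdominal pain (15) | Not stated | None stated |

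**2. Effect on a recorded rate.** Let p be the true rate, u the share unable to report, and s the chance that a nurse marks a true symptom present in such a patient. Assume no false positives and the same p in patients who can and cannot report. Then

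recorded rate = p × [(1 − u) + u × s].

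All three inputs are assumptions; u is varied around the more-than-50% capacity figure in section 12. For p = 20%:

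| u | s = 0 | s = 0.5 | s = 1 |
|---|---|---|---|
| 25% | 15.0% | 17.5% | 20% |
| 50% | 10.0% | 15.0% | 20% |
| 75% | 5.0% | 12.5% | 20% |

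For example, at u = 50% and s = 0.5: 0.20 × (0.5 + 0.5 × 0.5) = 0.15.

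**3. Effect on a between-arm difference.** If u and s are equal across arms, both rates are multiplied by the same factor. An assumed true 30% v 10% (20 points) is recorded as 15, 10 or 5 points at u = 25%, 50% or 75% with s = 0, and as 17.5, 15 or 12.5 points with s = 0.5. The ratio of rates stays at 3.

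**4. Could false positives cancel this?** Let f be the chance that a symptom-free non-reporter is marked present. The bias vanishes when p × s + (1 − p) × f = p, so f = p(1 − s)/(1 − p). At p = 20%:

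- s = 0: 0.20/0.80 = 25%
- s = 0.25: 0.15/0.80 = 18.75%
- s = 0.5: 0.10/0.80 = 12.5%

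False positives would have to be fairly common, so downward bias is the likelier direction.

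**5. Does restricting to assessable patients gain power?** Section 11.1 targets 30 per arm, so combined inulin v placebo is 60 v 30. At u = 50% the assessable patients are 30 v 15. Exact power of a pooled two-proportion z-test, two-sided 0.05, for assumed true rates:

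| True rates | All reported fully | All dosed, s = 0 | All dosed, s = 0.5 | Assessable only |
|---|---|---|---|---|
| 45% v 15% | 85% | 43% | 67% | 55% |
| 30% v 10% | 60% | 25% | 43% | 34% |

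Restriction beats the all-dosed analysis when nurses detect nothing in non-reporters, and loses to it when they detect half.

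**The case against.** A reader might infer that the plan scores sedated patients as symptom-free. It does not say so. No section assigns absent to a non-reporter, and the nursing impression in section 10.3.2 lets a nurse enter present from signs such as grimacing or guarding. The case report form is not in the documents and may carry a further option. This stands: under-recording is probable, not prescribed.

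Nor are nurses the only source. Section 10.3.2 provides for bedside assessment of the subject, so it does not follow that alert patients go unasked. What remains is that sections 10.3.2 and 13.3.1 differ on source.

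The capacity figure concerns consent around ICU admission. A patient without capacity may still say that something hurts, and section 12 has capacity reassessed at each interaction. It is a proxy only.

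Nurses are blinded (section 12.1), so no arm should be favoured unless alertness differs by arm. The numerical stopping boundary in section 17.4 concerns toxic death, and several other tolerability items remain. The Glasgow Coma Scale is recorded at each assessment (section 13.3), so a sensitivity analysis in responsive patients is already possible. However, that score describes one moment and the symptom question covers 24 hours, so it cannot fully separate a true absence from a patient who could not say.

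Finally, a denominator of assessable patients is defined after randomization and could itself differ by arm. This stands and shapes the fix.

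**Conclusion.** The concern holds for nausea and abdominal pain only. The plan codes two subjective symptoms as present or absent over all dosed patients, with no not-assessable category, while giving a comparable item in the same section exactly that category. In this population, rates and absolute differences are then probably biased towards zero.

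The size is not determined by the documents. With a true rate of 20% and half of patients unable to report, the recorded rate runs from 10% to 20% depending on nurse detection. This assumes no false positives and equal true rates in patients who can and cannot report.

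The stronger reading, that a separate code would restore lost power, is not supported: the direction of the power change depends on assumed detection and assumed event rates. The sound argument is a less biased rate in assessable patients and a visible count of those not assessed. The change should be made, because afterwards non-assessable patients cannot be reliably told apart from true negatives.

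**What to change.** - Add an *unable to assess* code for nausea and abdominal pain, matching bloating. Apply it to the whole 24-hour window, so that a symptom reported or observed earlier in the window still counts as present even if the patient is not alert at the assessment.
- Reconcile sections 10.3.2 and 13.3.1 so that alert patients are asked directly, and carry the same coding into section 15.
- Report the number assessable by arm and visit. Show rates among assessable patients beside rates over all dosed patients.
- Keep vomiting and obstruction on all dosed patients.

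The cost is one case report form code and one reporting rule. The drawbacks are a smaller denominator for two symptoms, possible loss of power in the restricted analysis if nurses detect many symptoms, and a denominator set after randomization. Showing both rates with the counts by arm lets readers judge the last of these.

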### 6.3. Inulin in the ambulatory setting

Inulin has been studied in over 400 ambulatory patients where it has shown excellent safety and tolerability. No serious adverse events have been reported in trials using doses up to 34 g/day inulin or 55 g/day mixed fiber, with self-resolving bloating the main side effect. Three trials specifically examined outcomes related to the ability of inulin to prevent colonization or infection. First, Dewulf *et al.* randomized 30 patients to inulin 16 g/day vs placebo; the inulin group had a doubling of *F. prausnitzii* and other SCFA-producers and concurrent decreases in serum CRP and LPS concentration. Second, Lecerf *et al.* randomized 60 volunteers 1:1:1 to placebo, a combination xylo-oligosaccharide (XOS), or inulin-XOS. The inulin group had the highest post-treatment SCFA levels and butyrate levels, the lowest circulating LPS, and decreased gene expression for the pro-inflammatory cytokines IL-1 $\beta$ , TNF $\alpha$ , and IL-12. Third, Miguez *et al.* found that an inulin-like fructo-oligosaccharides (FOS) preserved gut microbiome diversity after broad-spectrum antibiotics, mitigated loss of SCFA producers, and increased butyrate levels 3-fold. **Table 1** lists selected studies of inulin in the ambulatory setting, focusing on those with results most relevant to this project.

[figure not shown]

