## 13. Study assessments

The total study duration will be no more than 30 days of bedside assessments and no more than 6 months of telephone follow-up, both measured from the first recorded set of ICU vital signs. Samples will be gathered and bedside assessments made at the following intervals after ICU admission or until hospital discharge/death: baseline, 3 days, 7 days, 14 days, and 30 days. During study assessments, data will be combined from the following sources: (1) samples collected by the study team, (2) bedside assessments, and (3) data from the EMR.

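### Scheduled scoring of gastrointestinal tolerability covers about 48 of 168 dosing hours, so short episodes are under-counted in every arm

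*Combined protocol and SAP*

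**What the plan says.** Section 10.3.2 says the pre-specified adverse events will be actively sought and compared between arms, up to ICU Day 7 (the end of the intervention period) and also up to Day 30 or discharge. It then fixes the measurement windows:

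- Stool frequency is "measured by subject or nursing report by the number of spontaneous stools over the 24 hours preceding each assessment".
- Stool consistency is "measured by subject or nursing report as an ordinal variable (0-4) over the 24 hours preceding each assessment".
- Bloating is "measured by subject or nursing report as an ordinal variable (0-3) over the 24 hours preceding each assessment".

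For the other four symptoms 10.3.2 gives no window. Section 13.3.1 supplies it: nurses are asked about the "presence or absence of the following symptoms during the 24 hour period prior to each study assessment: nausea, vomiting, bowel obstruction, and abdominal pain". Section 15 agrees, since these events "will be recorded as present or absent for each assessment and separated from other AEs".

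Section 13 times the assessments from ICU admission, "or until hospital discharge/death: baseline, 3 days, 7 days, 14 days, and 30 days". Section 9.2.1 adds an assessment on the day of discharge for patients leaving before Day 14. Section 12.3 sets dosing at 14 doses, one every 12 hours. Section 6.3 summarises the ambulatory experience with inulin "with self-resolving bloating the main side effect".

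**The concern.** Section 5.2 gives feasibility and safety as the purpose of the trial, and the symptom scores go into the safety officer's reports. The side effect the protocol expects is one that goes away by itself, and such a symptom is easily missed by two spot checks in a week. The baseline window precedes the first dose, and Days 14 and 30 come well after dosing. No daily gastrointestinal score is specified, and no question covers the time since the previous assessment.

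Elsewhere the protocol does cover whole intervals. Section 15 summarises electrolytes over all 7 days of dosing, and 13.3.2 counts tube-feeding interruptions over the interval between assessments. As written, the symptom schedule does not deliver the follow-up that 10.3.2 describes. At stake are recorded intolerance rates that are too low in each arm, and reduced ability to see a tolerability difference between inulin and placebo.

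**Working it through.** **Inputs from the documents.** Doses: 14, every 12 h (12.3). Assessments: 0, 72, 168, 336 and 720 h after ICU admission (section 13). Look-back: 24 h (10.3.2 and 13.3.1). First dose: within 6 h of admission (sections 9, 11.1 and 11.2), or a goal of 24 h with a deviation only after 48 h (9.4; 12.2 repeats the 24 h goal). The timing statements must be reconciled, so each was tried.

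**Dosing period.** 14 × 12 h = 168 h = 7 days, which reproduces the protocol's figure.

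**Coverage.** The windows that can overlap dosing are 48–72 h and 144–168 h after admission. For a first dose at 0, 6, 24 or 48 h, both lie wholly inside dosing:

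- scored: 24 + 24 = 48 h, and 48/168 = 28.6%;
- unscored: 168 − 48 = 120 h = 5 days in total;
- doses given inside a window: 4 of 14.

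The total is constant, but its position is not. The first window opens 48, 42, 24 or 0 h after the first dose, for first doses at 0, 6, 24 and 48 h respectively.

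**Early discharge.** With the discharge-day assessment, a patient leaving on Day 4, 5 or 6 has about 2 of 4, 2 of 5 or 2 of 6 days scored.

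**Episodes missed (illustration).** Assume one episode of length L days, with onset uniform over the 7 dosing days and the first dose at admission. The windows are then days 2–3 and 6–7 of dosing. An episode is seen if onset falls between 2 − L and 3, or between 6 − L and 7, cut off at 0.

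| L | onset range seen (days) | seen | missed |
|---|---|---|---|
| 12 h | 1.5 + 1.5 = 3 | 3/7 = 43% | 57% |
| 1 day | 2 + 2 = 4 | 4/7 = 57% | 43% |
| 2 days | 3 + 3 = 6 | 6/7 = 86% | 14% |
| 3 days | 3 + 4 = 7 | 7/7 = 100% | 0% |

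**Sensitivity to the first dose.** A first dose at 24 h moves the windows to dosing days 1–2 and 5–6, and the last dosing day falls after the Day 7 assessment. For L = 1 the share seen is (2 + 2)/7, so 43% are still missed. For L = 2 it is (2 + 3)/7, so 29% are missed. For L = 3 it is (2 + 4)/7, so 14% are missed. At 48 h the windows are dosing days 0–1 and 4–5. The shares seen are 3/7, 4/7 and 5/7, so 57%, 43% and 29% are missed.

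**Effect on a comparison (illustration).** Assume true 1-day episode rates of 30% with inulin and 10% with placebo, and 4/7 seen. Recorded rates are 30% × 4/7 = 17.1% and 10% × 4/7 = 5.7%. The 20-point excess becomes 11.4 points, while the ratio stays at 3.

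**The case against.** The strongest reply is that section 15 deliberately limits monitoring to pre-specified events because complete recording is impractical in septic ICU patients, and that other routes span the gaps. REDCap has an Anytime form for events between assessments (section 14). Stopping for a related event counts as an unanticipated problem (12.3), and such problems are watched for in real time (15.2). The time and dose of every administration are recorded (9.4). Tube-feeding interruptions and calorie intake are indirect measures of tolerance. Section 15.2 also refers to a separate monitoring plan that was not available here.

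Much of this stands for serious, unforeseen or clinically obvious events. It does not supply arm-compared rates of mild, expected symptoms, which is what 10.3.2 sets out to give.

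A reader might infer more than the text supports:

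- *That events on the other days go unrecorded.* Only the scheduled scoring is missing; the routes above remain.
- *That symptoms in the first two dosing days are always missed.* This holds only if dosing starts at or very near ICU admission. With a first dose at 24 or 48 h, the Day 3 window falls on the second or first dosing day.
- *That only 2/7 of 1-day episodes are seen.* That fraction fits momentary events, or episodes aligned to whole scoring days. A 24-hour episode with onset at any hour is seen 4/7 of the time.
- *That Day 14 and Day 30 scores dilute the on-treatment summaries.* Section 10.3.2 already specifies a comparison up to Day 7, and extra scores cannot lower a patient's maximum. Only the pre-dose baseline score needs separating.
- *That the schedule favours inulin.* The windows are the same in all blinded arms.

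**Conclusion.** The point holds as a measurement weakness that is cheap to correct. For a patient in hospital through Day 7, scheduled gastrointestinal scoring covers about 48 of 168 dosing hours (29%). That follows from the documents for any permitted first-dose time. Which dosing days go unscored depends on that time, and patients discharged early gain one more window.

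The consequence is under-counting of short episodes in all arms, a smaller absolute difference and lower sensitivity to intolerance, with no built-in bias towards an arm. The size rests on assumptions: the documents give neither episode lengths nor symptom rates, and calling bloating self-resolving sets no duration. With uniform onset and a first dose at admission, about 43% of 1-day and 14% of 2-day episodes are missed and none of 3 days or more. A later first dose leaves the end of dosing after the Day 7 assessment, and the losses are then equal or larger. Nothing here shows that the trial would wrongly declare inulin well tolerated.

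**What to change.** At the Day 3 and Day 7 assessments, and at any earlier discharge assessment, change the look-back in 10.3.2, 13.3.1 and 15 to the interval since the previous assessment. At the first on-treatment assessment it should run from the first dose. Then:

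- Extend the existing EMR abstraction of stool frequency and consistency to each dosing day.
- Ask nurses whether nausea, vomiting, obstruction or abdominal pain occurred at any time in the interval. Add chart review as a new source, because 13.3.1 specifies EMR abstraction only for the stool items. Where dosing runs past the Day 7 assessment, continue the review to the last dose.
- Ask alert patients for their worst bloating in the interval.
- Keep the 24-hour score as well, so that the same-day measure is not lost.
- Leave the pre-dose baseline score out of the on-treatment mean and maximum in section 15.

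The cost is a change to protocol and CRF wording and some added chart review by existing staff. Interval recall is less exact than a 24-hour report and cannot be had from patients who are not alert. Section 12 expects more than half of patients to lack decision-making capacity, so this limit is real, but it applies equally in all arms. The change concerns measurement only and leaves clinical management untouched.
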